Adequacy of Sample Size: Optimal Design 2.0 Software⁵³ was used to conduct power analyses for hierarchical linear modeling (see C3) of treatment effects. An alpha level of .05 was chosen for each of the primary hypotheses. Given that our pilot research has found medium effect size (ES) on the higher end of the continuum for PTSD severity and medium ES for re-abuse severity (see C1), a more conservative medium ES (delta = .60; which is on the lower end of the continuum of medium effect sizes) was assumed in an effort to account for the potential for reduced effects in the current study. We also assumed an ES variability of .07 across the 6 shelters where recruitment will occur. An ES variance of .07 corresponds to a standard deviation of approximately .2, which for ES = .60 reflects substantial variation in treatment ES across shelters. Thus, we are powering the study to be able to detect a medium ES, even if there is substantial ES variability across shelters. Additional assumptions for the power analysis included a proportion of explained variance by the blocking variable (i.e., shelter) of .1 and a proportion of explained variance by the level 1 covariate (i.e., baseline PTSD or violence severity), of .3. There is little literature on which to base estimates of these two parameters for the proposed study, but these parameters have relatively little effect on sample size requirements given the specified ES, ES variability, and number of shelters. For example, the most extreme value of 0 (instead of .1) for the proportion of explained variance by the blocking variable would only increase the necessary sample size by 2 per shelter. Also, even an extreme value of .1 (instead of .3) for proportion of explained variance by the baseline level of the outcome variable would only increase the necessary sample size by 5 per shelter. Using the parameter estimates specified above and a desired power of .80, results of the

power analysis indicated that 25 participants were required per shelter for a total N of 150. In our pilot research we had retention rates of 81-95% (see C1). Thus, assuming the more conservative attrition rate of approximately 20%, we would need 31 participants per shelter, for a total of 186 participants to achieve a power of .80 to detect medium-sized treatment effects for our primary outcomes.

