Secondary outcomes will be assessed at all major time points. Since HOPE is associated with significant decreases in depression (see C1) and PTSD and depression frequently co-occur⁵⁹, depression will be assessed with the **Center for Epidemiological Studies Depression Scale (CESD⁶⁰)**. Additionally, given the established relationships between IPV and child abuse and maltreatment²² and mental health symptoms and child abuse potential in victims of IPV living in shelters⁴², we will also assess participants' child abuse potential with the brief form of the **Child Abuse Potential Inventory (CAPI⁶¹)**. The brief CAPI is a well validated and frequently employed measure that assesses 7 known correlates of child abuse (i.e., distress, family conflict, rigidity, happiness, feelings of persecution, loneliness, financial insecurity) without directly assessing violence towards children, making the measure acceptable to parents. The impact on quality of life (as both a secondary outcome and for cost analyses described in C3) will be assessed using the **Veterans SF-12 (VR-12)** (the U.S. government's public use variant of the SF-12)⁶². Our prior work found the VR12 discriminates well between the quality of life losses associated with different levels of PTSD⁶³. This research also found that Sengupta's HUI3 scoring⁶⁴ was the best of 50 existing scorings of the VR-12. That scoring measures functional status in quality-adjusted life years (QALYs), the quality of life measure routinely used in clinical trials of pharmaceuticals. Additionally, given that HOPE adopts an empowerment approach and a primary treatment goal is to increase participants' effective use of personal and social resources, the **Personal Progress Scale Revised (PPS-R)⁶⁵** will be used to assess empowerment, the **Social Support Questionnaire (SSQ⁶⁶)** will be used to assess degree and quality of social support, and the **Effectiveness in Obtaining Resources (EOR) Scale⁶⁷** will be used to assess perceived effectiveness in accessing community and shelter resources. Finally, as HOPE is a CBT that targets dysfunctional cognitions, the **Posttraumatic Cognitions Inventory (PTCI)⁶⁸** will be used to assess trauma-relevant cognitions.

Objective Measures of Stress Responding will be assessed at baseline, post-treatment, and 1-yr follow-up:

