Prior to conducting analyses for the main project aims, a series of routine procedures will be conducted to ensure the data accuracy/adequacy. We will also examine the distribution of our key variables for skewness, variability, missing data, and outliers. Data will be transformed to achieve normality if needed. At this time, we will also assess the effectiveness of the randomization procedures. If between-group differences exist, relevant variables will be included as covariates in outcome analyses. We will also explore whether contamination is a significant issue by comparing members of the control groups reporting they were exposed to specific HOPE content to those who were not exposed to determine if such exposure impacts outcome, and control for exposure in analyses below if necessary. Although only a small percentage of participants in our pilot work reported initiation of a new medication (3.3%), change in dose or type of ongoing medications (3.3%), or cessation of a medication (5%), we will also explore whether medication changes during treatment impacted outcome, and control for medication changes in analyses if necessary (see below). Additionally, we will preliminarily investigate therapist effects on attendance, attrition, and primary outcomes and use this data to inform future research with HOPE that will more directly assess therapist effects. Finally, pattern mixture methods^{74, 75} will be used to assess the ignorability of missingness in all outcome analyses described below. All analyses will include an intent-to-treat analysis (using data from all randomized participants) and a minimal attendance analysis (i.e., attending at least $\frac{1}{2}$ of sessions). For intent-to-treat analyses, missing data will be handled using multiple imputation with an expectation maximization algorithm.

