Primary and Secondary Outcomes: Hierarchical linear modeling (HLM) will be used to analyze the different trajectories that may occur between the two treatment groups. Separate HLMS will be conducted for all primary outcomes (i.e., PTSD and re-abuse severity), as well as for each secondary outcome. Additional time-varying (e.g., medication changes measured at multiple time points) and time-invariant covariates (e.g., length of shelter stay) that might explain additional variability in symptom level and change can also be modeled. Additionally, using the procedures described by Jacobson and Traux⁷⁶, the reliable change index will be computed for primary outcomes at 1-week post-treatment in order to assess whether the change in PTSD symptoms experienced by HOPE participants was clinically meaningful. Exploratory analyses will also be conducted to determine what constitutes an adequate dose of HOPE.

Other Secondary Outcomes: Mixed design ANOVAs will be used to analyze treatment effects for attentional biases and cortisol reactivity. Cortisol reactivity will be assessed by analyzing the area under the curve (AUC) of the reactivity curve. This will be computed in two ways: area under the curve with respect to increase (AUC_i) and area under the curve with respect to ground (AUC_G)⁷⁷. Mixed design ANOVAs that include a between-subjects factor (treatment group) and within-subjects factor (assessment time point) will be used to compare

both AUC_i and AUC_G values at each of the three time points as a function of treatment group. To evaluate treatment effects on attentional biases, we will conduct mixed design ANOVAs that include a between-subjects factor (treatment group) and within-subjects factors (e.g., word type; assessment time point). A group X word type X assessment time point interaction will be tested and deconstructed to determine, for example whether HOPE participants show reduced (relative to controls) attentional interference (i.e., less difficulty disengaging attention) to trauma-related stimuli (but not other types of stimuli) following treatment.

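### Cortisol reactivity and attentional bias are analysed with baseline as an outcome level rather than a covariate, which is valid but gives away precision

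*Combined protocol and SAP*

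**What the plan says.** Section C2 fixes the measurement schedule: "Objective Measures of Stress Responding will be assessed at baseline, post-treatment, and 1-yr follow-up". Table 1 agrees, so a baseline value exists by design for both the cortisol measures and the visual search task.

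Section C3 (Other Secondary Outcomes) then says: "Mixed design ANOVAs will be used to analyze treatment effects for attentional biases and cortisol reactivity". For cortisol, the between-subjects factor is treatment and the within-subjects factor is assessment time, and the ANOVAs compare "both AUC_i and AUC_G values at each of the three time points as a function of treatment group". For attentional bias, word type is added as a within-subjects factor: "A group X word type X assessment time point interaction will be tested and deconstructed". In both, baseline is one level of the outcome.

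No baseline covariate is named for either measure. The only covariate rule that reaches them is in the opening paragraph of C3: "If between-group differences exist, relevant variables will be included as covariates in outcome analyses". That rule is triggered by an observed imbalance and is not a planned adjustment for precision.

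**The concern.** In a randomized comparison, a baseline value that predicts the follow-up value can remove noise from the estimated treatment effect. Placing baseline among the outcome levels uses that information only through change from baseline, which subtracts the whole baseline value whatever its predictive strength. Comparing the arms at a single visit does not use it at all.

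At stake is the chance of missing a real effect, and the width of the intervals, on measures that section B5 presents as novel and highly relevant. No power calculation is given for them, so nothing in the plan shows that there is precision to spare. The imbalance-triggered rule does not help, because the gain from a prognostic baseline is there whether or not the arms happen to differ.

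**Working it through.** **The plan's own figure.** There is none for these two measures. The only calculation (C2, Adequacy of Sample Size) concerns the primary outcomes: "An alpha level of .05 was chosen for each of the primary hypotheses". Its inputs are 6 shelters, effect size .60, effect-size variance .07, shelter explaining .1 and baseline explaining .3 of the variance, and power .80. For a multisite trial, with n per shelter,

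λ = 6 × .60² / [.07 + 4(1−.1)(1−.3)/n].

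At n = 25 this is 2.16 / (.07 + .1008) = 12.65. On F(1, 5) the power is .809, and 25 is the smallest n that reaches .80. The stated 150 is therefore reproduced, and 150/186 = 80.6% retention fits the assumed attrition of about 20%. This gives 75 analysable women per arm for the illustration below. The plan takes credit here for a baseline covariate, but only for PTSD and violence severity.

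**Which contrast the ANOVA delivers.** The C3 wording for cortisol allows two readings: a group × time effect, which at a given follow-up visit is the difference in change from baseline, or separate comparisons of the arms at each visit. Both are checked. For the search task the formulas apply to one score, such as an interference contrast at one visit. They were not derived for the omnibus three-way interaction.

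**Variances.** Assume one follow-up visit, equal variances at baseline and follow-up, and correlation ρ. Relative to the unadjusted single-visit comparison (= 1):

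- change from baseline: 2(1−ρ)
- baseline-adjusted: 1−ρ²
- ratio of adjusted to change: (1−ρ²)/[2(1−ρ)] = (1+ρ)/2

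| ρ (assumed) | Change | Adjusted | Adjusted ÷ change | Adjusted ÷ single visit | Extra women needed by change scores |
|---|---|---|---|---|---|
| .3 | 1.40 | .91 | .65 | .91 | 1/.65 − 1 = 54% |
| .5 | 1.00 | .75 | .75 | .75 | 33% |
| .548 | .905 | .70 | .774 | .70 | 29% |
| .7 | .60 | .51 | .85 | .51 | 18% |
| .8 | .40 | .36 | .90 | .36 | 11% |

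The row at .548 is √.3, borrowed from the explained variance assumed for the primary outcomes. It is not a figure for cortisol or the search task.

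**Power at one visit**, with 75 per arm, two-sided .05 and an assumed standardised effect of 0.4:

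| ρ | Change | Single visit | Adjusted |
|---|---|---|---|
| .3 | .54 | .69 | .73 |
| .5 | .69 | .69 | .81 |
| .548 | .73 | .69 | .83 |
| .7 | .89 | .69 | .93 |

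At ρ = .548 the effect detectable with 80% power is 0.435 for change, 0.457 for a single visit and 0.383 with adjustment.

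**Validity.** A simulation of 6,000 trials per scenario, with three equally correlated visits and no treatment effect, gave type I error between .048 and .055 for both the ANOVA and the adjusted analyses. With an effect of 0.4 at both follow-ups, the group × time test had power .56, .76 and .91 at ρ = .3, .548 and .7. Adjustment at the first follow-up alone gave .71, .83 and .93.

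**The case against.** The strongest defence is that the planned ANOVA is a legitimate analysis under randomization. It holds its error rate, the outcomes are secondary, and B5 asks change questions (normalised cortisol reactivity, reduced bias) that a baseline level displays directly. The first two parts stand. The third stands only as a point about presentation: once baseline is a covariate, the adjusted difference in follow-up values and the adjusted difference in change are the same number.

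It is also fair to say that the size of the loss depends on an unknown correlation and is modest when that correlation is high: at ρ = .7, power is .89 against .93. This stands.

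Four stronger readings may tempt a reader and are not supported:

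- *That the ANOVA discards women with a missing visit.* The opening of C3 plans multiple imputation for every intent-to-treat analysis and pattern-mixture checks for all outcome analyses, so a complete-case count does not describe the planned analysis.
- *That the treatment effect is diluted by averaging over baseline.* This would be true of a group main effect, but nowhere is the main effect named as the deciding test.
- *That both measures rest on a 2-df group × time test.* For attentional bias the named test is the three-way interaction. With four word types and three visits it has (2−1)(4−1)(3−1) = 6 df, and is then broken down.
- *That moving these measures to the plan's hierarchical linear model would cure the problem.* That model is described as comparing trajectories and does not itself name a baseline covariate. The covariate has to be written in.

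**Conclusion.** The point holds as one of efficiency. Cortisol AUC_i, AUC_G and attentional bias are analysed with baseline as an outcome level and without a routine baseline covariate, although the baseline is collected. Adjustment gives a smaller variance than either reading of the plan for every ρ strictly between 0 and 1. Against change scores the reduction is (1−ρ)/2: 35%, 25% and 15% at ρ = .3, .5 and .7. Against an unadjusted single-visit comparison it is ρ²: 9%, 25% and 49%.

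These sizes assume equal variances and one follow-up visit. The correlation is an assumption throughout, since the documents give none for these measures, and the gain over change scores vanishes as ρ nears 1. The power figures also assume an effect of 0.4. There is no bias, type I error is preserved, and the enrolment of 186 is unaffected. The change is worth making because it costs so little, not because the planned analysis is invalid.

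**What to change.** In C3, Other Secondary Outcomes, replace the mixed-design ANOVAs as follows.

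- **AUC_i and AUC_G:** fit a mixed model to the post-treatment and 1-year values, with the baseline-visit value of the same measure as an explicit covariate, categorical visit, group, and group × visit. Report the adjusted group difference with its interval at each visit. State that the covariate is the AUC from the baseline assessment, because C2 also uses the word baseline for the saliva sample taken before the video cue.
- **Search task:** use the same structure, adding word type and its interactions with group and visit. The covariate is the baseline value for the corresponding word type, or the baseline interference contrast. Define the interference score in advance.
- **Adjustment rule:** include the baseline covariate whether or not the arms are seen to differ.
- **Keep** the planned multiple imputation and pattern-mixture checks, and report change from baseline descriptively.

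The cost is one extra covariate per model and the decision on how to score interference. No new data or visits are needed.

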Attentional Biases in PTSD will be measured using a visual search task (VST) with a lexical decision component recently used in research assessing attentional biases in PTSD. Four different word types (i.e., trauma, general threat, semantically-related neutral, uncategorized neutral words) and "non-words" matched for word length and perceived frequency of usage will serve as stimuli for the VST. Stimuli will be presented on computer monitor using E-Prime software and response latencies will be recorded by the computer. Participants will first be presented with a fixation cross. They will then be presented with the stimulus screen which includes four letter strings in a rectangular array, with one (the "oddball") being the target stimulus. Participants are instructed to indicate as quickly and as accurately as possible whether the target is a word or non-word by pressing one of two keyboard keys.

To standardize diurnal influences on cortisol levels, assessment of cortisol reactivity will occur between the hours of 4PM and 7PM. After participants arrive at the assessment, they will sit quietly and complete the least invasive interview materials during the first half-hour of the interview. This is done to reduce the influence of travel and novelty of the assessment on cortisol levels. Following this rest period, participants will watch a 5-min clip of a video depicting IPV. This video will serve as the trauma cue. Using Salivettes sampling device (Sarstedt, Newton, NC), four saliva samples will be collected at 0 (baseline: prior to trauma cue), 15, 30, and 45 minutes after the 5-min video clip. Saliva samples will be stored at -80° C until assay. Saliva samples will be processed at the Center for Psychosomatic Research (Trier, Germany) using a time resolved immunoassay with fluorescence detection (DELPHI)⁶⁹.

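### The attention-bias analysis names only a 6-df three-way interaction for a focused pattern; one baseline-adjusted planned contrast, not conditional on the omnibus test, would be a cheap improvement

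*Combined protocol and SAP*

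**What the plan says.** Section C3, Other Secondary Outcomes, analyses the visual search task by mixed-design ANOVA with treatment group between subjects and word type and time point within subjects. The only test it names is this: "A group X word type X assessment time point interaction will be tested and deconstructed to determine, for example" whether HOPE participants, relative to controls, have less trouble disengaging from trauma words, and from no other kind, after treatment.

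Section C2 defines the levels: "Four different word types (i.e., trauma, general threat, semantically-related neutral, uncategorized neutral words"). The task is given at baseline, post-treatment and 1 year (C2, Objective Measures of Stress Responding; Table 1). Section B5 states the aim more broadly, as reduced bias towards threat cues in general.

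The sample-size section concerns other outcomes. It says "An alpha level of .05 was chosen for each of the primary hypotheses", and the 186 women are enrolled "to achieve a power of .80 to detect medium-sized treatment effects for our primary outcomes". No effect size, alpha or power is given for the visual search task.

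**The concern.** An omnibus interaction spreads its sensitivity over every way in which the arms could differ across word types and visits. The pattern that C3 describes occupies a small part of that space. The text also leaves open how the two steps relate, and each reading has a cost.

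- If the interaction must be significant before it is broken down, or is the only formal test, a real trauma-word effect can miss significance and be reported as no effect.
- If the breakdown goes ahead regardless, neither the word types compared nor the visit is fixed, and the one pattern given is only an example. The contrast that gets emphasised can then be chosen after seeing the means.

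What is at stake is the interpretation of one secondary outcome. The primary conclusions on PTSD and re-abuse are not affected.

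**Working it through.** **The plan's own figure.** Section C2 (Adequacy of Sample Size) assumes ES .60, ES variance .07 over 6 shelters, and explained variance of .1 (shelter) and .3 (baseline). For a multisite trial with random shelter effects, noncentrality = 6 × .60² / [.07 + 4(1 − .1)(1 − .3)/25] = 2.16/.1708 = 12.65. On F(1, 5) this gives power .81, so 25 per shelter (N = 150) is reproduced. I use 150 evaluable women, 75 per arm; 186 × .8 = 148.8 is consistent with that.

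**Degrees of freedom.** (2 − 1) × (4 − 1) × (3 − 1) = 6.

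**Dilution.** Assumptions: two-sided alpha .05 (stated only for the primary hypotheses), sphericity, and all of the signal in one contrast. For a standardised difference d on the contrast score, noncentrality λ = (75/2)d² = 37.5d². I test the same λ on F(1, 148) and on F(6, 888).

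| d | λ | 1 df | 6 df | loss (points) |
|---|---|---|---|---|
| .30 | 3.38 | .45 | .23 | 22 |
| .40 | 6.00 | .68 | .40 | 28 |
| .46 | 7.94 | .80 | .52 | 28 |
| .50 | 9.38 | .86 | .61 | 25 |
| .60 | 13.50 | .96 | .79 | 16 |
| .67 | 16.83 | .98 | .89 | 10 |

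The largest loss at any effect is 28.4 points. The multivariate form, F(6, 143), gives .51 in place of .52 at λ = 7.95. Where the single contrast has power .90 (λ = 10.65), the omnibus test has .67. To regain .80 on 6 df, λ must rise from 7.95 to 13.72, a factor of 1.73 in sample size. If non-words were analysed as a fifth level, there would be 8 df and the loss at .80 would be 33 points.

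**Does a concrete contrast do better?** The score is trauma minus the mean of the two neutral types at 1-week post-treatment, adjusted for the same score at baseline. Assumptions: unit residual SD for each word-type-by-visit mean, independent across word types, correlation ρ between visits, and an effect of .40 SD.

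- Score variance: 1 + 1/2 = 1.5. After baseline adjustment it is 1.5(1 − ρ²). At ρ = .4, λ = 37.5 × .16/(1.5 × .84) = 4.76, power .58 on F(1, 147).
- Omnibus: λ = 37.5 × .16 × S/(1 − ρ), where S is the interaction sum of squares of the pattern. For trauma words only, at both later visits, S = 3/4 × 2/3 = .5. If general-threat words respond equally, S = 1 × 2/3 = .667. At ρ = .4, λ = 5.00 and 6.67, power .32 and .43 on F(6, 143).

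| ρ | trauma minus neutral (either pattern) | omnibus, trauma only | omnibus, trauma and threat |
|---|---|---|---|
| 0 | .51 | .20 | .26 |
| .4 | .58 | .32 | .43 |
| .6 | .70 | .48 | .62 |

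The gain vanishes when the effect is large and the visits are strongly correlated: at .65 SD, ρ = .6, with threat words also responding, both tests have .98.

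**Why neutral words are the reference.** If threat words respond and the reference is all three other types, the effect shrinks to .40 × 2/3 = .267 and the variance is 4/3. At ρ = .4, λ = 37.5 × .0711/(1.333 × .84) = 2.38, power .33, which is below the omnibus .43.

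**The case against.** Four points can be made for the plan.

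1. A reader might infer that the hypothesis is exactly one trauma-word contrast and that the other five degrees of freedom are irrelevant. The documents do not support that. C3 offers the trauma-word pattern as an example, and B5 speaks of threat cues more widely. This stands. It bears on which contrast to choose, and trauma minus all others would be a poor choice.
2. A reader might infer that the omnibus test is a stated gate. It is not: C3 says the interaction will be tested and deconstructed, without making the second step conditional on the first. This also stands, so the power loss is conditional. It does not rescue the plan, because an ungated breakdown with no named contrast is open to selection after the fact.
3. A flat loss of 30 points would overstate the matter. With four word types, 28 is the ceiling, and it needs the contrast to carry all the signal. The .80 reference power belongs to the primary outcomes.
4. The outcome is secondary, carries no power claim, and mixed ANOVA followed by decomposition is conventional. This stands and limits the importance of the point.

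**Conclusion.** The point holds as a cheap improvement to a secondary analysis. The only named attention-bias test has 6 df, and the pattern it is meant to detect is focused. If the omnibus test is a gate or the sole test, the cost is at most about 28 points of power (.80 to .52), and about 10 to 28 points for contrast effects of d = .30 to .67. If it is not a gate, the weakness is an unspecified contrast.

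The figures rest on alpha .05, 150 women evaluable on the task, sphericity, four word types and an assumed range of effects, since the documents supply no effect size for this task. The comparison for the trauma-minus-neutral score also depends on an assumed between-visit correlation. In the cases tabulated, that score does better than the omnibus test whether or not general-threat words respond, by 8 to 31 points.

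**What to change.** Before unblinding, amend C3 as follows.

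- **Main attention-bias test:** one score per woman, mean latency for trauma words minus mean latency for the two neutral word types, at 1-week post-treatment. Compare arms with adjustment for the same score at baseline. State that the test does not depend on the omnibus interaction.
- **Durability:** repeat the comparison at 1 year.
- **Specificity:** report general-threat minus neutral and trauma minus general-threat in the same way. Together these address both the trauma-specific pattern in C3 and the wider threat wording in B5.
- **Omnibus:** report the 6-df interaction as descriptive.

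The cost is SAP wording; no new data are needed. The downside is that a pattern outside these contrasts would only be described.

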
Drs. [name] and [name] have previously collaborated in a study investigating salivary cortisol levels in IPV victims⁴⁵. Using similar methodology as proposed here in which 4 salivary samples were collected over a 1-hour period (see C2), the cortisol awakening response was investigated in a sample of 52 shelter residents. Results suggested that IPV-related PTSD severity was associated with significantly greater cortisol output the first hour after waking. Thus, pilot data support the use of cortisol response within S-IPV victims as well as the ability of the research team to successfully collect multiple saliva samples from shelter residents.

C2. Study Design: To test our hypotheses that HOPE will significantly reduce severity of IPV-related PTSD and re-abuse in S-IPV victims compared to PCT, we plan to enroll 186 residents of battered women shelters with IPV-related PTSD into a prospective randomized controlled trial comparing HOPE to a attention-matched control condition (i.e., PCT). Residents of battered women shelters meeting study eligibility (see below) will be randomized into one of the two study arms. Participants will be offered 16 sessions of therapy (see Figure 1), either HOPE or PCT, beginning while women are in shelter (0-10 sessions) and continuing until 3-months post-shelter (6-16 sessions). The number of sessions attended within the shelter environment is dependent on participants' length of shelter stay, with a maximum of 10 sessions in shelter. Participants will then complete the remaining 6-16 sessions of HOPE outside of shelter. Therapy sessions will occur in shelter or another convenient, safe, and confidential location. Participants will be blinded to whether or not they received the investigative treatment or control condition. Blinded outcome assessments will be administered 1-week post-shelter treatment, 1-week post-shelter, and 1-week, 6-months, and 1-year-post-treatment.

Figure 1. Proposed model for delivery of treatment and assessment of outcome.

*Participants who are still in shelter after their 10th session will participate in monthly booster sessions.

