The cost effectiveness analysis (CEA) measure will be cost/QALY gained, computed as [intervention cost minus direct cost savings]/QALYs saved. We will follow widely accepted CEA guidelines^{78,79}, including computing estimates from societal and government perspectives, adjusting future costs to present value with a 3% discount rate, and analyzing how sensitive the results are to higher and lower discount rates. Most intervention costs will be tracked in the project accounting system. The exception is the cost of social services with PCT versus HOPE. To estimate these costs, we will track the number of visits by type of service, then price those visits using average service prices. We are not powered to and will not try to track medical costs, especially since some domestic violence injuries can have lasting medical consequences. Instead, we will use our existing violent injury cost model⁸⁰⁻⁸³ and sexual violence costs⁸⁴ to cost each injury type tracked in our CTS data, then sum and compare the estimated costs of the injuries in the control versus the treatment groups. We will rely on published costs of depression by severity^{85,86} to compute the savings from reduced depression. These sources include direct medical and mental health care costs, as well as long-term QALY losses and life table effects. The evaluation data will record short-term employment impacts. The QALY measures partially incorporate those impacts so we will take care not to double count. Following guidelines,^{78,87} we will count employer savings due to reduced presenteeism of employed people who reduced their depression through HOPE as direct costs, using presenteeism impacts from Stewart⁸⁸. Using Oracle's Crystal Ball Excel add-in, we will enter uncertainty ranges for all parameters in the cost/QALY calculation. From that information, we will develop a Cost-Acceptability Curve that determines the probability that HOPE is preferred to standard care as a function of the value of a QALY. One third of all cost/QALY analyses now take this approach to uncertainty analysis⁸⁹ and we have guidelines exist on how to interpret the results.

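### The cost-per-QALY formula does not make intervention cost incremental to PCT, and the acceptability curve names a comparator that is not a trial arm

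*Combined protocol and SAP*

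**What the plan says.** The cost-effectiveness paragraph of C3 gives the measure as "intervention cost minus direct cost savings]/QALYs saved". On the cost side it says "Most intervention costs will be tracked in the project accounting system", and then "The exception is the cost of social services with PCT versus HOPE". It does not say which arm or arms the accounting figures cover, or whether PCT is netted out.

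On the savings side, the plan will "sum and compare the estimated costs of the injuries in the control versus the treatment groups". For depression it will use published costs by severity "to compute the savings from reduced depression", with no comparator named. QALYs come from the VR-12; under the secondary outcomes in C2, the chosen scoring is described thus: "That scoring measures functional status in quality-adjusted life years (QALYs".

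The same C3 paragraph ends with a curve for "the probability that HOPE is preferred to standard care as a function of the value of a QALY".

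The design in C2 has two arms: "Participants will be offered 16 sessions of therapy (see Figure 1), either HOPE or PCT".

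**The concern.** A cost-per-QALY ratio can be interpreted only if its costs, savings and QALYs all refer to the same comparison. Here the QALY difference and the injury savings are HOPE against PCT. The delivery cost is not tied to any contrast, and the curve refers to a third condition that the trial does not include.

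An analyst working from C3 could enter the whole cost of HOPE. HOPE would then carry the cost of a course of therapy while being credited only with what it adds to another course of therapy with the same number of sessions offered. The ratio would be too high, and the acceptability curve, built from the same calculation, would inherit the error. Alternatively, the analyst could net out PCT and then report the curve as evidence against standard care, which the data do not address.

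This matters beyond one table. B5 lists the cost-effectiveness analysis among the study's innovations, and the closing statement of section D makes a cost-effective model program the ultimate goal.

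**Working it through.** **1. Are the arms matched on sessions offered?** C2 allocates 93 women to each arm and offers each woman 16 sessions: 93 x 16 = 1,488 sessions per arm. Five percent is .05 x 1,488 = 74.4. The Adherence and Competence paragraph of C2 states 74 HOPE and 74 PCT sessions, so the plan's own figure reproduces and confirms the match on sessions offered. Therapist qualifications (C2, Therapists) and the two-day workshop (C2, Therapist training procedures) are also alike. PCT delivery therefore has a real cost.

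**2. Which contrast does each component use?**

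| Component | Contrast given in C3 |
|---|---|
| Delivery cost | not stated |
| Social services | PCT versus HOPE |
| Injury savings | control versus treatment |
| Depression savings | not stated |
| QALYs | not stated; observable only against PCT |
| Acceptability curve | HOPE versus standard care |

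**3. Size of the discrepancy.** Let C_H and C_P be delivery cost per woman in HOPE and PCT, S the direct cost savings, and dQ the QALYs gained over PCT, with S and dQ both on the HOPE-PCT contrast.

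- Gross reading: (C_H - S)/dQ
- Incremental reading: (C_H - C_P - S)/dQ
- Difference: C_P/dQ

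The numerator is off by C_P and the ratio by C_P/dQ. This does not require equal delivery costs in the two arms. If the cost entered is already incremental, the difference is zero.

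**4. Illustration.** The documents give no session cost and no QALY gain, so those values are assumptions. The 12.7 sessions are the pilot mean for expanded HOPE (C1, Acceptability and Feasibility), applied here to PCT for want of PCT data.

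- C_P: 12.7 x $75 = $952.50; 12.7 x $150 = $1,905
- Low end: $952.50/.05 = $19,050 per QALY
- High end: $1,905/.02 = $95,250 per QALY

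Wider assumptions (12.7-16 sessions, $50-150 per session, dQ of .01-.10) give:

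- Low end: 12.7 x $50 = $635, and $635/.10 = $6,350 per QALY
- High end: 16 x $150 = $2,400, and $2,400/.01 = $240,000 per QALY

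**5. Can the reading change the conclusion?** Assume 16 sessions at $100 in both arms ($1,600 per woman) and dQ = .05.

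- S = $0: gross $1,600/.05 = $32,000 per QALY; incremental $0.
- S = $500: gross $1,100/.05 = $22,000 per QALY; incremental -$500/.05 = -$10,000 per QALY, so HOPE would be cost-saving.

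**The case against.** The strongest reply is that the plan never says HOPE is charged in full. Intervention cost is undefined. The one cost item singled out is framed as PCT versus HOPE, which fits an incremental reading, and C3 says accepted guidelines for such analyses will be followed. PCT is delivered inside the project, so nothing shows that its costs would go unrecorded. All of this stands, so the overstatement has to be put conditionally. The guidelines are cited without their content, and what C3 spells out from them (perspectives and discounting) does not settle the numerator.

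It can also be said that standard care may loosely mean PCT, since the rationale in C2 describes supportive therapy as part of many practitioners' usual practice. But C1 and C2 use the standard-care and standard-services wording for shelter care alone, the pilot control. At best the term is ambiguous. If shelter care is meant, full HOPE cost could be the right numerator, but savings and QALYs measured against PCT would then not match it.

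Several stronger inferences are tempting and are not supported:

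- That HOPE costs almost nothing more than PCT. The documents match sessions offered, not sessions attended or total resources. HOPE also involves collaboration with shelter staff (B2) and a workbook and customized handouts (C2, Potential for Cross-Contamination).
- That every saving is measured against PCT. Only the injury comparison says so; the contrast for depression and presenteeism savings is unspecified.
- That the ratio is off by the cost of the PCT sessions. That is the possible excess in the numerator; the ratio would be off by that cost divided by dQ.

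Finally, this is a supplementary analysis. It touches no primary outcome and no sample size, which limits its weight but does not make the definition coherent.

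**Conclusion.** The concern holds as a problem of definition. A reader might infer that the plan is biased against HOPE as written; the text does not establish that, because it does not say that intervention cost is gross. What it does establish is that neither reading gives a consistent result. With a gross cost, numerator and denominator describe different contrasts and the ratio is overstated by C_P/dQ. With an incremental cost, that error is zero, but the curve still cannot support a statement about standard care.

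The illustrative excess of about $19,000-95,000 per QALY rests on assumed session costs and QALY gains and on HOPE pilot attendance standing in for PCT attendance. The wider range of $6,350-240,000 shows how little the documents fix its size. The illustration shows only that the choice can change the economic conclusion, so it should be settled before analysis.

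**What to change.** In C3, name PCT as the comparator for both the ratio and the acceptability curve, and define the measure per randomized woman as:

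[(HOPE delivery cost - PCT delivery cost) - (direct cost savings of HOPE relative to PCT)] / (QALYs in HOPE - QALYs in PCT)

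State that the depression and presenteeism savings use the same contrast as the injury savings. Record delivery costs by arm in the project accounting system, and exclude research-only costs from both arms. If a result against standard care is wanted, label it a modelled secondary analysis, with costs, savings and QALYs all on that contrast.

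The cost is one revised formula and separate cost codes for PCT, best set up before delivery begins because costs not separated at the time are hard to recover. No further data are needed from participants. The drawback is that the main curve no longer speaks directly to standard care.
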